6.7 Assessment and Treatment of Allergic Reactions to Peanut OIT

6.7.1 Assessment of the Severity of Acute Allergic Reactions to Peanut OIT

Subjects may develop allergic symptoms during the course of OIT, similar to those that may occur during other desensitization protocols (eg, venom immunotherapy, drug desensitization, desensitization to aeroallergens by subcutaneous injection). The severity of the reaction will be determined on the basis of the investigator's judgment. The following definitions, developed to be consistent both with the PRACTALL consensus report on DBPCFC and with the CoFAR grading system for allergic reactions, are provided as a general guide.

Mild symptoms:

- Skin – limited (few) or localized hives, swelling (eg, mild lip edema), skin flushing (eg, few areas of faint erythema), or pruritus (eg, causing mild occasional scratching)
- Respiratory – rhinorrhea (eg, occasional sniffling or sneezing), nasal congestion, occasional cough, throat discomfort
- GI – mild abdominal discomfort (including mild nausea), minor vomiting (typically a single episode), and/or a single episode of diarrhea

Moderate symptoms:

- Skin – systemic hives (eg, numerous or widespread hives), swelling (eg, significant lip or face edema), pruritus causing protracted scratching, more than a few areas of erythema, or pronounced erythema
- Respiratory – throat tightness without hoarseness, persistent cough, wheezing without dyspnea
- GI – persistent moderate abdominal pain/cramping/nausea, more than a single episode of vomiting and/or diarrhea

Severe symptoms:

- Skin – severe generalized urticaria/angioedema/erythema
- Respiratory – laryngeal edema, throat tightness with hoarseness, wheezing with dyspnea, stridor
- GI – severe abdominal pain/cramping/repetitive vomiting and/or diarrhea
- Neurological – change in mental status
- Circulatory – clinically significant hypotension ([Appendix 3](#))

6.7.2 Assessment of the Tolerability of an Individual Dose of IP

Determination of the tolerability of any individual dose of IP should be based on an assessment of acute symptoms occurring in close temporal succession to dosing.

In general, the severity of allergic symptoms elicited at a particular dose of IP will define the tolerability of that dose of IP. The place where there is the greatest need for clinical judgment in determining the tolerability of a dose is when the dose elicits mild allergic symptoms. **Table 4** illustrates the likely combinations of symptom severity and tolerability.

Table 4 Allergy Symptom Severity and IP Dose Tolerability

Symptom Severity	Assessed Tolerability
None	Tolerated
Mild, oropharyngeal symptoms only	Tolerated
Mild, meeting pre-defined tolerability criteria (Section 6.7.1)	Tolerated ^a
Mild, not meeting pre-defined tolerability criteria (Section 6.7.1)	Not tolerated
Moderate (except for rare exceptions, Section 6.7.1)	Not tolerated
Severe	Not tolerated

^a Mild, persistent gastrointestinal symptoms lasting several days may be not tolerated ([Section 6.7.3.1](#)).

In general, the severity of an allergic reaction will correspond to the maximum severity of any of its symptoms.

No symptoms: If a dose elicits no symptoms, the dose will be assessed as tolerated.

Mild symptoms: When dosing with IP elicits an acute reaction characterized by the appearance of only a mild symptom(s), the investigator will be required to assess whether the dose was or was not tolerated. The determination of tolerability must be made on the basis of clinical judgment. The following are presented as guidelines for determining whether a dose associated with the emergence of a mild symptom or symptoms was tolerated. A dose eliciting only mild symptoms may be considered to be tolerated if the symptoms are:

- Isolated to a single organ system
- Resolve with no pharmaceutical intervention or with a single oral administration of an H1 antihistamine
- Do not require administration of epinephrine
- Are not worsening in intensity or distribution over time
- Resolve, or shows definite signs of resolving, in under 1 hour
- Do not include objective wheezing

Based on experience from Phase 2 studies, most acute allergic responses to dosing that are characterized by mild symptoms would be anticipated to meet the above criteria. If, however, an allergic response to dosing is characterized by mild symptoms that do not meet all of the above criteria (eg, has mild symptoms occurring in 2 or more organ systems, requires treatment with 2 doses of antihistamine or 1 dose epinephrine, shows progression in severity or distribution over time, is protracted in duration, or includes objective wheezing), then even though the allergic symptoms may be mild, the dose should be assessed as not tolerated. If a dose elicits mild symptoms that do not fit all of the above criteria and the dose is assessed to

be tolerated, then a brief explanation as to why the dose was considered tolerated must be recorded in the CRF.

Moderate symptoms: In general, if a dose elicits moderate symptoms, the dose will be assessed as not tolerated. However, there may be rare occasions when a dose eliciting moderate symptoms could be assessed as tolerated. This would only be the case for a transient, self-limited (requiring no intervention and resolving completely) symptom occurring in a single organ system. In addition, the symptom would be typically subjective only. Any dose associated with moderate symptoms and assessed as tolerated must be accompanied by a brief explanation in the CRF as to why the dose was considered tolerated.

Severe symptoms: In nearly all cases, if a dose elicits severe symptoms, the dose will be assessed as not tolerated. Whenever a dose elicits an allergic response characterized by 1 or more severe symptoms, the crucial decision, after adequate treatment for the allergic reaction has been administered, will be to determine whether the subject should continue in the study, dosing at a reduced dose level, or be discontinued early from the study.

The determination of tolerability will decide the course of action to be taken in response to dose-related reactions ([Section 6.7.3](#)).

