6.3.3 Up-dosing Period

The Up-dosing Period will last approximately 20 (to a maximum of 40) weeks and comprise 10 scheduled Up-dosing Visits (including the first 300 mg dose of the Maintenance Period), with the potential for Unscheduled Visits for assessment of dose tolerability, dose-reduction, dose re-escalation, or management of AEs.

Subjects will return to the clinic every 2 weeks for up-dosing to a maximum daily dose of 300 mg. The first dose of IP at each new dose level will be administered in the CRC under direct observation and medical supervision.

Subjects must be free from active wheezing, a flare of atopic disease (eg, atopic dermatitis), or suspected intercurrent illness prior to any dose escalation. Subjects should be maintained on their current, or a reduced, dose level of IP until their flare of asthma, atopic disease, or intercurrent illness has resolved.

Subjects should withhold their daily home dose of IP on in-clinic dosing days, but should take all other prescribed medications as scheduled.

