- Any subject deemed to have **severe symptoms** that include hypoxia, hypotension, or change in mental status (stage 3 anaphylaxis defined in [Appendix 3](#)), or who receives intensive therapy (to be determined by the investigator, but may include such interventions as IV epinephrine, intubation, or admission to an intensive care unit) for an allergic reaction at any time should be discussed with the medical monitor and discontinued from the study.
- On the day following in-clinic up-dosing, the site is to make telephone contact with the subject/subject's parent or guardian to enquire if any AEs (including allergic symptoms) occurred subsequent to the subject leaving the clinic, and to provide assistance in the recording of any such events in the diary.
- A dose escalation attempt may be postponed 1 to 2 weeks if, in the clinical judgment of the investigator, the current dose level has not been sufficiently well tolerated to proceed to the next dose level.
- If an investigator suspects that a subject has not tolerated, or is not tolerating, his or her current dose level, the investigator should have the subject return to the clinic to determine whether a dose reduction is warranted, and if so, the magnitude of the reduction. The investigator may also decide to maintain the current dose or to withhold dosing. Guidelines for setting the new, lower dose are outlined in [Section 6.7.5](#), with the dose adjustment depending on the severity of the dose-related symptoms.
- Subjects who require dose reduction during a 2-week dosing period will have their escalation schedule reset, as necessary, to maintain the new dose level for a 2-week period prior to attempting to re-escalate.
- Following a dose reduction, it is advised that an escalation attempt be made by 4 weeks, unless escalation is to be delayed further due to administration of epinephrine, as defined in [Section 6.7](#). Failure to successfully escalate after 3 consecutive attempts, with each attempt spaced at least 2 weeks apart, will result in the cessation of dosing. The subject will be asked to return to the CRC 14 to 16 days following the last dose of IP to undergo an Early Discontinuation Visit ([Section 6.4](#)) and is to be followed for safety in the interim.
- For symptoms occurring during the Maintenance Period, the same study dosing rules and guidelines that apply for the Up-dosing Period will also apply.

6.3.3.2 80 mg Up-dosing Visit

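### In Up-dosing, a mild non-oropharyngeal reaction needing exactly two antihistamine doses is not tolerated under Section 6.7.2 (default: step down), while Section 6.7.6 and Table 6 let escalation continue

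*Protocol*

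**What the plan says.** Section 6.7.2 lists criteria under which a dose that causes only mild symptoms may count as tolerated. One of them is that the symptoms "Resolve with no pharmaceutical intervention or with a single oral administration of an H1 antihistamine". Among its examples of failing the criteria is a reaction that "requires treatment with 2 doses of antihistamine or 1 dose epinephrine"; "then even though the allergic symptoms may be mild, the dose should be assessed as not tolerated". If the investigator still calls such a dose tolerated, "then a brief explanation as to why the dose was considered tolerated must be recorded in the CRF". Table 4 in the same section has a separate row under which mild symptoms confined to the oropharynx are tolerated, and 6.7.5.1 says much the same of oral or pharyngeal pruritus. The section closes: "The determination of tolerability will decide the course of action to be taken in response to dose-related reactions".

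Section 6.7.5 makes a reduction of one or two levels the default for a dose judged not tolerated, but also lists holding the current level for a further 1 to 2 weeks. For mild symptoms judged not tolerated, 6.7.5.1 specifies a one-step reduction, given in the clinic the next day. Section 6.3.3.1 lets the investigator maintain the dose or withhold it when tolerability is in doubt.

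Sections 6.7.5.1 and 6.7.5.2 both refer sites to 6.7.6 for dose adjustment after antihistamines. There, the text says that escalation can go on if only antihistamines were given. It asks for a reduction of one or two levels if more than two antihistamine doses were needed on an up-dosing day, or if an antihistamine was combined with another drug other than epinephrine. The Table 6 row for antihistamines alone says to continue escalating and mentions neither a dose count nor a severity. Section 6.7.7 applies the Up-dosing guidelines to Maintenance.

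**The concern.** The same mild reaction meets two different thresholds. A site that judges tolerability first will, at two antihistamine doses, treat the dose as not tolerated and by default step the child down. A site that goes to the treatment rule, as 6.7.5.1 and 6.7.5.2 direct, finds that two doses do not trigger a reduction. It keeps the dose and goes up at the next visit. That site may also see no reason to write the CRF explanation that 6.7.2 requires, because 6.7.6 does not mention it.

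This is a dosing-safety rule for children aged 4 to 17 who take a known allergen daily. What is at stake is consistent dose adjustment between sites and a usable record of why a dose was kept.

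**Working it through.** No figure in the protocol depends on this point, so the check sets the rules side by side and then sizes the difference from the dosing schedule.

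**1. The rules by number of antihistamine doses** (Up-dosing, mild reaction other than isolated oropharyngeal symptoms, no other drug):

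| Doses | 6.7.2, then 6.7.5.1 | 6.7.6 text | Table 6 row |
|---|---|---|---|
| 1 | may be tolerated if the other criteria are met | continue | continue |
| 2 | not tolerated unless explained in the CRF; default one-step reduction | continue (2 is not more than 2) | continue |
| 3 or more | not tolerated unless explained in the CRF; default one-step reduction | reduce by 1 or 2 levels | continue (limit appears only in the text below the table) |

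The rules agree at one dose and conflict at two. At three or more, only the table row, read alone, is out of line.

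**2. Does counting per day instead of per dose remove the conflict?** Section 6.7.6 counts antihistamines over an up-dosing day, while 6.7.2 judges a single dose of study product. At an Up-dosing Visit one dose is given, and "Subjects should withhold their daily home dose of IP on in-clinic dosing days". The two counts therefore cover the same dose, and the conflict stays.

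**3. Severity.** Section 6.7.6 allows antihistamines alone for moderate symptoms. Section 6.7.2 lets a moderate reaction pass as tolerated only for a "transient, self-limited (requiring no intervention and resolving completely) symptom occurring in a single organ system". The Table 6 row carries no such restriction.

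**4. Difference in the next day's dose.** Ratio of each Table 2 level to the one below it:
6/3 = 2.00; 12/6 = 2.00; 20/12 = 1.67; 40/20 = 2.00; 80/40 = 2.00; 120/80 = 1.50; 160/120 = 1.33; 200/160 = 1.25; 240/200 = 1.20; 300/240 = 1.25.
The range is 1.20 to 2.00.

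**5. Delay if the default reduction is taken.** Under 6.7.6 the next new level comes at week 2. Under 6.7.2 and 6.7.5.1 the child spends h weeks at the reduced level and then 2 weeks at the original level, so the next new level comes at week h + 2. The delay is (h + 2) − 2 = h weeks.
- Section 6.7.5.1 gives h as at least 1 to 2 weeks.
- Section 6.3.3.1 gives h = 2, since children whose dose is reduced "will have their escalation schedule reset, as necessary, to maintain the new dose level for a 2-week period prior to attempting to re-escalate".
- Section 6.3.3.1 also advises an escalation attempt by 4 weeks, so h is up to 4.

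Spare time in Up-dosing is 40 − 20 = 20 weeks (Sections 3.2 and 6.3.3). One such event uses 1/20 = 5%, 2/20 = 10% or 4/20 = 20% of it.

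**6. Maintenance.** The two readings give 300 or 240 mg/d, a difference of 300 − 240 = 60 mg/d (ratio 1.25). No further escalation is involved.

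**The case against.** The best defence is that the sections can be read in order. Tolerability is judged first, and 6.7.2 says that this judgment decides the action. Section 6.7.5.1 also asks for it before pointing to 6.7.6, and the note under Table 5 points back to 6.7.2. On this reading, 6.7.6 means only that antihistamine use does not by itself bar escalation of a tolerated dose. The 6.7.2 criteria are guidelines subject to clinical judgment, 6.7.6 is permissive, and the medical monitor is available for questions.

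Much of this stands. It shows which section should govern and that a step-down is a default, not an obligation. It does not reconcile the thresholds. If 6.7.2 governs, the more-than-two trigger in 6.7.6 comes too late for mild reactions, because a reduction is already the default at two doses. No sentence ranks the sections, and two cross-references send sites to 6.7.6 for this decision.

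Three further points limit the concern:
- A reader might infer that every mild reaction needing two antihistamine doses is affected. Table 4 and 6.7.5.1 treat isolated oropharyngeal symptoms separately, so those are outside it.
- A reader might infer that 6.7.6 waives the CRF explanation. It does not; it is silent, and the requirement in 6.7.2 still applies.
- The unlimited Table 6 row might be read as permission to escalate after any number of doses or after any moderate reaction. The explanatory text below the table supplies the dose limit, and 6.7.2 and 6.7.5.1 deal with moderate reactions explicitly. The row is incomplete; it is not a separate policy.

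**Conclusion.** The conflict is real but narrow: mild reactions other than isolated oropharyngeal symptoms, needing exactly two antihistamine doses, in Up-dosing or Maintenance, with no documented exception. Section 6.7.2 should govern, so the 6.7.6 threshold is the one to correct.

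The size assumes that one site takes the default reduction and another continues. The next day's dose then differs by one level, a ratio of 1.20 to 2.00. In Up-dosing the next new level is delayed by about 1 to 2 weeks, at most 4 on the advised timing. Where the investigator holds the dose instead, the next-day difference disappears and only a delay remains.

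A reader might go further and infer a bias in the primary endpoint. A route exists: under 6.7.5.1, a mild not-tolerated dose followed by two reduced doses that are also not tolerated makes the child an escalation failure, which Section 9.2.1 counts as a treatment failure. But the protocol gives no frequency for such reactions, so no effect can be derived, and it is probably small. The Exit DBPCFC is scored under its own, stricter rule in Section 6.6, where mild symptoms needing any drug treatment are dose limiting. The point should be corrected as a dosing-safety inconsistency. It does not touch eligibility, sample size or analysis.

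**What to change.** In the antihistamine paragraph of 6.7.6 and the matching row of Table 6, state: *Escalation continues only if the dose is assessed as tolerated under Section 6.7.2, including Table 4; otherwise follow Sections 6.7.5 and 6.7.5.1.*

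Change the reduction trigger in 6.7.6 from more than two antihistamine doses to two or more. Allow two exceptions: isolated oropharyngeal symptoms assessed as tolerated (Table 4 and 6.7.5.1), and a tolerated assessment explained in the CRF as 6.7.2 requires. Without the first exception, the new trigger would itself contradict Table 4.

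Add that for mild reactions the first action is the one-step reduction of 6.7.5.1, and keep the options to hold or maintain the dose in 6.3.3.1 and 6.7.5. Leave 6.7.4 unchanged: its allowance of one or two antihistamine doses belongs to Initial Escalation.

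The cost is one paragraph, one table row and a training note to sites. The downside is a few more step-downs, each taking about 1 to 2 weeks (up to 4) of the 20 spare Up-dosing weeks.

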6.7.3 Assessment of the Tolerability of a Dose Level

6.7.3.1 Assessment of Acute Symptoms Occurring After Dosing

With the report of moderate or severe symptoms occurring during home-dosing, the dose level should be considered to be not tolerated and the subject brought to the clinic the day after the emergence of the symptoms for administration of the next dose under medical supervision. If a dose administered at home is suspected to have been not tolerated, even on the basis of mild symptoms, the subject should also return to the CRC for dosing under medical supervision.

The recurrence of a mild symptom(s) over the course of several days of home-dosing should suggest that the dose level is not tolerated, even if each individual occurrence of symptoms could be assessed as tolerated, on the basis of the criteria listed in [Section 6.7.2](#).

- If the site is notified of mild dose-related symptoms on 4 or more occasions during a 7-day period, the subject should return to the CRC for dosing under direct observation for assessment of the tolerability of the dose level.
- If mild dose-related symptoms are noted on 7 or more occasions during a 2-week dosing interval at a given dose level, that dose level should be considered not tolerated and appropriate action should be taken ([Section 6.7.5.2](#)).

Because of the reduced reliability inherent in the second-hand reporting of symptoms, investigators are strongly encouraged to have subjects return to the clinic to undergo dosing under direct observation whenever acute allergic symptoms associated with dosing are reported.

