6.7.5 Treatment for Reactions During the Up-dosing Period: Dose Adjustment

If a dose or dose level is assessed as *not tolerated*, the action taken will depend on the type and severity of the dose-related reaction and the investigator's clinical judgment. The following possible actions are at the investigator's disposal and are considered in greater detail in subsequent sections ([Section 6.7.5.1](#), [Section 6.7.5.2](#), and [Section 6.7.5.3](#)):

- Dosing the subject under medical supervision in the CRC – this is encouraged whenever there is question as to the tolerability of a dose level. It may be performed at the current dose level or at a reduced dose level if there is already a high index of suspicion that the current dose level has not been tolerated.
- Holding dose level at current level for an additional 1 to 2 weeks before attempting dose escalation – this may be done at the discretion of the investigator if there is concern that the current dose level has not been sufficiently well tolerated to attempt up-doing to the next dose level.

[figure not shown]
- Reducing dose by 1 or 2 dose levels and maintaining the reduced dose level for at least 1 to 2 weeks before attempting dose re-escalation – Generally, this should be the action taken when a dose that has been observed in the CRC is assessed as not tolerated, if a dose elicits moderately severe symptoms, or if the investigator is convinced of the intolerance of the current dose level. In short, it should be considered the default action whenever a dose or dose level is assessed as *not tolerated*.
- Reducing dose level for less than the usual 2-week period – this may be instituted as treatment for an intercurrent AE, to aid the investigator in determining if a dose level is or is not tolerated, or if a pattern of decreased IP tolerability during menses is discerned. The level of the reduction in dose, ranging from a 1-step reduction to a 50% reduction will be at the investigator's discretion, based on clinical judgment. The manner in which dose escalation may resume will depend on the level and the duration of the dose reduction.

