6.7.5.2 Reactions to Dosing at Home

With the occurrence of symptoms of an acute reaction to IP after home-dosing, or any acute allergic reaction, subjects or parents/guardians are instructed to call the study site. The investigator must then determine whether or not the dose was tolerated ([Section 6.7.3](#)). Because of the reduced reliability inherent in the second-hand reporting of symptoms, investigators are strongly encouraged to have subjects return to the clinic to undergo dosing under direct observation whenever acute allergic symptoms associated with dosing are reported.

When symptoms of a dose-related allergic reaction are reported during the course of daily home-dosing, the investigator must assess the severity of the reaction and whether the dose associated with the reaction was tolerated. The appropriate intervention will depend on the type and severity of symptoms ([Figure 3](#)).

In general, moderate or severe symptoms will be considered clinically significant, and any dose eliciting such symptoms *assessed as not tolerated*; however, mild symptoms may also be considered clinically significant (eg, if affecting multiple organ systems, increasing in

intensity, occurring with increasing frequency, or affecting a larger area over time) and *assessed as not tolerated*. Whenever there is question as to the clinical significance of mild signs or symptoms, the investigator should have the subject return to the CRC for observed dosing under medical supervision.

For home-doses *assessed as not tolerated* on the basis of acute dose-related symptoms, the same procedures described in [Section 6.3.3](#) for adjusting up-dosing should be followed. Dose adjustment after administration of antihistamines or epinephrine for dose-related allergy symptoms is described in [Section 6.7.6](#).

The recurrence of mild symptoms over the course of several days of home-dosing should suggest that the dose level is not tolerated, even if each individual occurrence of symptoms could be assessed as tolerated on the basis of the criteria listed above. In this circumstance, investigator judgment will be required to determine the best course of action with the possible actions being the following:

[figure not shown]
- Continue with daily home dosing at the current dose level
- Continue the same daily dose for the rest of the 2-week interval, with the dose split into 2 fractional doses given 8 to 12 hours apart (the 2 fractional doses need not be equal)

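### Section 6.7.3.1 classes a dose level with 7 or more mild-symptom occasions in 2 weeks as not tolerated, but the list it leads to in Section 6.7.5.2 still offers the same home dose

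*Protocol*

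**What the plan says.** Section 6.7.3.1 sets two counts for recurrent mild symptoms during home dosing.

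- **Four in 7 days.** If the site is told of mild dose-related symptoms "on 4 or more occasions during a 7-day period, the subject should return to the CRC for dosing under direct observation". This bullet states its own action and refers to no other section.
- **Seven in 2 weeks.** "If mild dose-related symptoms are noted on 7 or more occasions during a 2-week dosing interval at a given dose level", then "that dose level should be considered not tolerated and appropriate action should be taken", with a reference to Section 6.7.5.2.

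Section 6.7.5.2 takes up the same situation: "The recurrence of mild symptoms over the course of several days of home-dosing should suggest that the dose level is not tolerated". It then says that "investigator judgment will be required to determine the best course of action with the possible actions being the following". The first item in the list is "Continue with daily home dosing at the current dose level". The second keeps the same total daily dose, split into two. Later items are repeat dosing in the CRC under observation, a reduction of one or two steps, the 4-week hiatus and discontinuation.

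Two other places bear on a level classed as not tolerated. Section 6.7.5 says of a reduction by 1 or 2 levels that "it should be considered the default action whenever a dose or dose level is assessed as" not tolerated. An earlier sentence of Section 6.7.5.2 sends home doses assessed as not tolerated on acute symptoms to the up-dosing adjustment procedures of Section 6.3.3.

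**The concern.** A numerical trigger is useful in a dosing protocol because it takes one decision out of case-by-case judgment: once the count is reached, every site treats the level in the same way. Here the 7-in-2-weeks count produces a classification, but the section named for the resulting action reopens the question. Its list begins with two options that a reader would expect only for a level still regarded as tolerated.

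What is at stake is mainly consistent safety handling of children who react repeatedly at home. The choice also feeds the number of dose reductions and the time taken to reach 300 mg/d, and Section 6.7.7 carries the same dosing rules into the Maintenance Period. The discretion is likely to be used more in one arm. In ARC001 (Section 1.2.1), treatment-emergent hypersensitivity events occurred in 90% of AR101 subjects and 50% of placebo subjects.

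**Working it through.** The protocol gives no figure to reproduce on this point. The check is a comparison of text, followed by a short illustration of scale.

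**Step 1: follow the 7-in-2-weeks case through the protocol.**

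| Place | What it gives for this child |
|---|---|
| 6.7.3.1, second bullet | Level should be considered not tolerated; go to 6.7.5.2 |
| 6.7.5.2, paragraph on recurrent mild symptoms | Investigator chooses from a list; items 1 and 2 keep the full daily dose at home |
| 6.7.5.2, sentence on home doses assessed as not tolerated | Go to 6.3.3 |
| 6.3.3.1 | Return to clinic to decide whether to reduce; maintaining or withholding the dose is also possible |
| 6.7.5 | Reduction by 1 or 2 levels is the default |

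The list paragraph in 6.7.5.2 opens almost as the matching paragraph of 6.7.3.1 does, so it is the natural destination of the cross-reference. It names neither count and excludes no option once a count is reached. Its reduction item also refers back to 6.7.5.2 itself, so it gives no further direction.

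**Step 2: follow the 4-in-7-days case.** Section 6.7.3.1 says "the subject should return to the CRC for dosing under direct observation for assessment of the tolerability of the dose level". No cross-reference changes that. But the same child also meets the description in 6.7.5.2 of symptoms recurring over several days, and there observed dosing is only one of the possible actions. The two texts overlap, and neither says which prevails.

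**Step 3: compare with a weaker trigger.** Section 6.7.3.1 also says that a home dose merely suspected of not being tolerated, even on mild symptoms, should bring the subject back for supervised dosing. Suspicion of one dose thus leads to observation, while a level already considered not tolerated reaches a list whose first two items require none.

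**Step 4: scale, for illustration only.**

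- If each occasion belongs to a different daily dose (an assumption), 7 / 14 = 50% of the doses in the interval produced symptoms.
- Assume a one-level reduction held for 1 to 2 weeks (6.7.5), then 2 weeks again at the original level (Table 2). If the count is reached at the end of the interval, the delay is 2 + (1 to 2) + 2 − 2 planned = 3 to 4 weeks. If it is reached at day 7, the delay is 1 + (1 to 2) + 2 − 2 = 2 to 3 weeks.
- The slack in up-dosing is 40 − 20 = 20 weeks, so one such episode uses 2 / 20 = 10% to 4 / 20 = 20% of it. Continuing at the same home dose uses none.

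The protocol does not say what share of subjects would reach either count.

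**The case against.** The strongest reply is that the texts can be read together. The list in 6.7.5.2 has a broader and weaker trigger: recurrence that should suggest non-tolerance although each occurrence could be assessed as tolerated. Continuing at home is coherent for recurrences below the counts, while the specific rules of 6.7.3.1 would govern once a count is met. Section 6.7.5.2 also asks for observed dosing when the clinical significance of mild symptoms is in question, strongly encourages clinic return whenever acute symptoms are reported, and sends not-tolerated home doses to 6.3.3. The default in 6.7.5 is introduced as a general rule, and that section makes the action depend on clinical judgment.

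Much of this stands. The wording throughout is advisory, and there is more observed-dosing language than the list alone suggests. But the harmonising reading is not written down, and 6.7.3.1 itself sends the 7-or-more case to 6.7.5.2. The 6.3.3 sentence concerns home doses assessed as not tolerated, whereas the list concerns recurrences whose individual doses could each pass. The two routes compete, and the text does not rank them. Figure 3, which 6.7.5.2 cites for the choice of intervention, is not shown in the text available here. If it settles the recurrent-mild case, the text should say so.

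Two stronger readings are tempting and are not supported:

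- A reader might infer that the cross-reference cancels both counts. Only the 7-in-2-weeks bullet carries it; the 4-in-7-days bullet keeps its own action and merely overlaps with the list.
- A reader might infer bias or lost responders in the primary analysis. Section 3.2 keeps site personnel blinded to assignment. A delay of 2 to 4 weeks within 20 weeks of slack does not by itself make a subject a failure, and the first dose at each new level is supervised (6.3.3), so a later increase is not an unobserved one.

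**Conclusion.** The inconsistency is real, and its firmest part is the 7-in-2-weeks case: the level is classed as not tolerated in one section, and the section cited for action offers the unchanged home dose without saying that this option has lapsed. The 4-in-7-days case is a weaker overlap of the same kind. As written, sites can treat identical reaction histories differently and all be compliant.

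This is a safety-consistency point that should be corrected because the correction is specific and cheap. The conclusion rests on the text of Sections 6.3.3.1, 6.7.3.1, 6.7.5 and 6.7.5.2, and on Figure 3 not already resolving it. The delay figures assume a one-level reduction and a single episode. Neither the frequency nor any effect on the primary endpoint is shown. Which action is clinically right is not judged here.

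**What to change.** Reconcile Sections 6.7.3.1, 6.7.5 and 6.7.5.2, including the reference to 6.3.3.

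1. In 6.7.5.2, state for each count (4 or more in 7 days; 7 or more in a 2-week interval) which listed options remain available once it is reached. The clinical team decides which action applies.
2. Say whether a level classed as not tolerated by count follows the list, the 6.3.3 procedures or the default in 6.7.5, and replace the list item that refers 6.7.5.2 back to itself.
3. If continuing the current dose at home remains possible after a count is reached, require a short reason in the CRF. Section 6.7.2 already requires an explanation when a dose outside the mild-symptom criteria, or one with moderate symptoms, is judged tolerated.
4. Check that Figure 3 agrees with the result.

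The cost is protocol wording and one CRF comment field. Sample size and the primary analysis do not change.
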